1.0 Study Summary

Study Title	iThrive WI – A mobile health intervention to lower overdose risk and promote COVID-19 vaccine education amongst people who use drugs
Brief Summary	This study will examine if the use of a smartphone application called Thrive4Life Connect can help people who use drugs lower their risk of overdose and learn more about COVID-19 vaccines.
Number of study sites	3 – Vivent Health offices located in the cities of Milwaukee, Eau Claire, and Appleton, WI
Study Design	The mobile health system used in this study, called Thrive4Life Connect, has been developed for use in harm reduction settings by our team with prior funding from the National Institute on Drug Abuse. Thrive4Life Connect is based on the Addiction Comprehensive Health Enhancement Support System (A-CHESS) and facilitates brief, behavioral interventions targeting knowledge gaps, motivation, and social connectedness. This app is being used in another IRB-approved study at UW-Madison (Study ID: 2017-0866). In the proposed study, we will develop new intervention content for assessing and increasing vaccine confidence and lowering overdose risk. We will test the feasibility and preliminary effectiveness using a pilot, pre-post study design with 60 people who have injected drugs in the past week and used opioids in the past 30 days. We will examine feasibility outcomes based on study recruitment, retention, and intervention completion. We will also examine changes in knowledge about COVID-19 and overdose, motivation to reduce risk, and behavioral outcomes including overdose risk behaviors and vaccine uptake to establish preliminary effectiveness.
Primary Objective	To test the feasibility of a mobile health application, Thrive4Life Connect, to deliver an intervention focused on reducing overdose risk and supporting COVID-19 vaccine uptake among people who use drugs in Wisconsin.
Secondary Objective(s)	To understand overdose risk, COVID-19 vaccine uptake, and related attitudes and behaviors before and after the mobile health intervention.

PROTOCOL TITLE: iThrive WI – A smartphone intervention for overdose and risk and COVID-19 among people who use drugs

Research Intervention(s)/ Investigational Agent(s)	COVID-19 and overdose-related content contained within Thrive4Life Connect, a mobile health application
Drugs/devices used on study (including any IND/IDE #)	N/A
Study Population	Adults who have used opioids in the past 30 days and injected drugs in the past week, primarily recruiting among clients of Vivent Health
Sample Size	60 people
Study Duration for individual participants	6 months

Study Specific Abbreviations/ Definitions:

HIV	Human immunodeficiency virus
PN	Prevention Navigator
PS	Prevention Specialist
PWID	People who inject drugs
ROI	Rural Opioid Initiative
SSP	Syringe service programs
UW	University of Wisconsin

2.0 Background

2.1 We are now approaching the third year of the COVID-19 pandemic, which collided with a worsening, ongoing overdose epidemic that killed 9,260 people in Wisconsin from 2000-2019 from opioid overdose alone. Consistent with national and state-level trends indicating increases in fatal and nonfatal overdoses,^{1,2} overdose mortality in Wisconsin increased by 27% during 2020 relative to 2019³ Unfortunately, provisional 2021 data suggest it will be the deadliest year for drug overdose deaths in Wisconsin and the US.³ Beyond exacerbations to overdose mortality, prior studies also suggest that COVID-19 itself has disproportionately impacted people who use drugs, and that low vaccine confidence may continue to drive poor outcomes. Studies have shown that people who use drugs are at increased risk for COVID-19 infection, hospitalization, and death.⁴ Regarding vaccination, a survey of people who inject drugs in Wisconsin conducted by our team in March-May 2021 indicated that 50% of respondents were hesitant to be vaccinated for COVID-19, consistent with prior studies.⁵

Our team is well-positioned to support people who inject drugs (PWID), during the collision of a worldwide COVID-19 pandemic and the US overdose epidemic as we have conducted multiple prior studies in collaboration and partnership with Vivent Health, the state's primary network of syringe services programs. Our research will describe how mHealth interventions can reduce overdose and COVID-19 risk at a critical time of climbing overdose mortality in Wisconsin.

2.2 **Preliminary studies - Mobile health Interventions with PWID:**

[name] and his research team have conducted several mobile health (mHealth) interventions among individuals with active substance use disorders that provide a strong theoretical basis for the proposed work and highlight our team's ability to use mobile phones to collect rich behavioral health data from this population. Hep-Net, a UW-ICTR-funded pilot study designed to increase readiness to be tested for hepatitis C and respond to an overdose,^{6,7} showed the feasibility of a brief, computerized intervention involving individualized goal setting in the syringe services setting. We then studied the benefits of the Addiction Comprehensive Health Enhancement Support System (A-CHESS)⁸ within multiple treatment settings, including opioid use disorder treatment⁹ and HIV treatment (DP2DA042424).¹⁰ A-CHESS is guided by self-determination theory,^{11,12} which identifies three supports for intrinsic motivation for behavior change derived from basic psychosocial needs: relatedness (meaningful relationships with others; a sense of connectedness), competence (ability to deal with challenges), and

PROTOCOL TITLE: iThrive WI – A smartphone intervention for overdose and risk and COVID-19 among people who use drugs

autonomy (sense of being in control of one's own behavior and goals). A-CHESS also operationalizes the situated Information-Motivation-Behavioral Skills (sIMB) Model,¹³ by providing Information (e.g., available community resources), Motivation (e.g., a weekly survey about health goals), and Behavioral Skills (e.g., messaging with a counselor).

Existing Research Infrastructure to be Leveraged in The Proposed New Research:

WI Rural Opioid Initiative - Formative Phase (UW-Madison

IRB Study ID: 2017-0866: The Rural Opioid Initiative is a national, multi-site research consortium funded by NIDA, CDC, SAMHSA, and the Appalachian Regional Commission. The Wisconsin node of the consortium (grant numbers UG3DA044826 and UH3DA044826, [name] and [name], MPI) is built on an academic-community partnership with Vivent Health. In 2018-19, during the initial, formative (UG3) phase of this study, we enrolled 991 PWID from six rural counties in Wisconsin using the best available methods to ascertain a population-representative, cross-sectional sample of a hard-to-reach population.¹⁴⁻¹⁶ We included individuals aged 15 or above, who injected drugs within the past 30 days, and resided in Brown, Outagamie, La Crosse, Marathon, Douglas, or Eau Claire counties. Through Audio Computer-Assisted Self-Interviews,¹⁷ participants reported sociodemographic characteristics, substance use behaviors, overdose history and risk behaviors, and were tested for HIV, viral hepatitis, and sexually transmitted infections.

WI Rural Opioid Initiative - Intervention Phase (UW-Madison

IRB Study ID: 2017-0866: We are currently in the intervention (UH3) phase of the WI Rural Opioid Initiative, which involves a clinical trial of a short-term intervention, “prevention navigation,” to increase use of preventive health services and reduce risks from injecting drugs for PWID utilizing syringe services programs. Prevention navigation is based on Project START, an evidence-based, six-session, individualized case management intervention that was found to reduce HIV risk among recently incarcerated men using motivational interviewing techniques and a harm reduction framework.^{18,19} Our current trial adapted the Project START model for syringe services program settings. Clients receiving the intervention build skills and set goals to reduce their overdose, HIV, and hepatitis C risk, increase their readiness to engage in addiction and hepatitis C treatment, and address other areas of concern such as smoking and self-stigma. We are currently enrolling PWID in a non-randomized, clinical trial in the same syringe services program offices that participated in the formative phase of the study. Over 12

PROTOCOL TITLE: iThrive WI – A smartphone intervention for overdose and risk and COVID-19 among people who use drugs

weeks, intervention recipients complete 4 sessions lasting 50-70 minutes each wherein a “prevention navigator” uses strategies including linkage-to-care case management, peer navigation, motivational enhancement, formative decision making, and harm reduction to help participants develop an individualized risk reduction plan related to their injection drug use. Outcomes at 3 and 6 months among the 270 total intervention participants will be compared with data from 135 control participants, all of whom are recruited from the same sites involved in the formative phase. Analyses will compare two primary outcomes between intervention and control participants: confidence in ability to access addiction treatment services when participants are ready for treatment and engagement in addiction treatment services.

An additional activity supported by the intervention phase of the WI Rural Opioid Initiative is the development of Thrive4Life Connect, a novel harm reduction mHealth application that adapts A-CHESS for PWID accessing syringe services programs at Vivent Health. Thrive4Life Connect is guided by similar theoretical frameworks as A-CHESS (i.e., self-determination theory^{11,12} and the sIMB¹³). The Thrive4Life Connect app will be used by all participants to complete study surveys moving forward.

2.3 COVID-19 exacerbated a worsening overdose epidemic,²⁰⁻²² resulting in a 27% increase in overdose deaths in Wisconsin in 2020 relative to 2019.²³ Factors hypothesized to contribute to increased overdose mortality during the pandemic include an unsafe illegal drug supply contaminated with illicitly manufactured fentanyl,²⁴ increasing drug use while alone (i.e., away from potential overdose responders) due to physical distancing,²⁵ and deteriorating mental health.²⁶ These data indicate a need for targeted overdose risk reduction efforts to reduce the behavioral health impacts of COVID-19.

2020 and 2021 are the deadliest years for overdose on record nationally and in Wisconsin. Consistent with national trends,^{22,24-26} a COVID-19 impact survey conducted by our team among PWID in Wisconsin between March and May, 2021 found that increases in overdose risk behaviors may be driving overdose mortality upwards. In total, 52% of PWID used alone more often (i.e., away from potential overdose bystanders who could respond), 52% were concerned about the safety of the drug supply, 27% overdosed, and >75% reported greater depression, anxiety, and loneliness during the pandemic.

PROTOCOL TITLE: iThrive WI – A smartphone intervention for overdose and risk and COVID-19 among people who use drugs

COVID-19 vaccine hesitancy may exacerbate health disparities among PWID. People who use drugs, especially those with an opioid use disorder and racial/ethnic minorities, are at increased risk for COVID-19 infection and poor outcomes (e.g., hospitalization, death).²⁷ Unfortunately, like other studies,²⁸ 50% of PWID we recently surveyed were hesitant to be vaccinated for COVID-19. PWID are also under-vaccinated for other infections (e.g., hepatitis A and B²⁹) and lack access to preventive services.³⁰ To address disparities, interventions targeting upstream social determinants of health (i.e., stigma, social isolation, distrust in healthcare, food and housing insecurity) are needed. These may improve use of preventive services and change behaviors that ultimately cause health disparities, including those from COVID-19 and overdose.

3.0 Study Objectives and Endpoints

- 3.1** The primary objective of this study is to understand the feasibility of using a smartphone application to deliver an intervention focused on overdose and COVID-19. The secondary objective is to understand overdose risk, COVID-19 vaccine uptake, and related attitudes and behaviors before and after the intervention.
- 3.2** We hypothesize that an intervention to increase COVID-19 vaccination and reduce overdose risk will be feasible to deliver via a smartphone based on intervention completion rates. We also hypothesize that engaging with intervention content may increase knowledge about COVID-19 and overdose and reduce risk behaviors.
- 3.3 Study Endpoints:**
 - **Baseline:** At the beginning of the study, participants will complete a baseline survey to assess their pre-study overdose and COVID-19 risk behaviors, attitudes, beliefs, and knowledge. These data will be used as a basis to assess change at 3 months and 6 months.
 - **3-Months:** After the 12-week Thrive4Life Connect mobile intervention, participants will complete the same survey questions from baseline at 3 months to assess any changes in their overdose and COVID-19 risk behaviors, attitudes, beliefs, and knowledge. We will also examine the percentage of participants who completed intervention content each week, and the percentage of skipped intervention content questions to examine feasibility.
 - **6-Months:** 3 months after the 12-week mobile intervention, participants will again complete the same survey at 6 months to assess any changes in their overdose and COVID-19 risk behaviors, attitudes, beliefs, and knowledge. The 6-month survey will help us to

PROTOCOL TITLE: iThrive WI – A smartphone intervention for overdose and risk and COVID-19 among people who use drugs

understand whether any behavior changes from 3-months were sustained.

3.4 Participants who express any type of mental or other distress (e.g., thoughts of self-harm, harm to others, reports of child or elder abuse) based on any communications with the study team (e.g., by private message through Thrive4Life Connect, on the Thrive4Life Connect discussion board, via text or phone call with the study team, or any other way) will be engaged by study staff and connected with resources through Vivent Health or other means (e.g., National Suicide Prevention Hotline). The participant will be reminded that they can stop study participation at any time. Participants in significant distress may be removed from the study by research team staff.

4.0 Number of Participants

4.1 This study will include 60 participants in total across 3 Vivent Health syringe services locations in Wisconsin – Milwaukee, Appleton, and Eau Claire.

- Milwaukee: 30 participants
- Appleton: 15 participants
- Eau Claire: 15 participants

4.2 In a prior longitudinal study with Vivent Health (WI Rural Opioid Initiative - Intervention phase), we have experienced up to 50% attrition at 3 months and 6 months. Because of this, we may enroll up to 90 participants in this study.

4.3 Enrolled participants are individuals who complete the baseline survey. Participants who leave the study early (i.e., before completing the 3-month study assessment) may be replaced.

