13.2 Schedule of Procedures and Study Outline

This study will involve required and optional procedures.

Required activities include:

- Thrive4Life Connect
- Surveys
 - Baseline survey
 - 12 weekly check-in intervention surveys about overdose prevention
 - 3-month survey
 - 9 daily check-in surveys
 - 6-month survey
- Surveys will collect information about: Name, age, gender identity, ZIP code, race and ethnicity, education, marital status, alcohol and drug use, types of health care received, mental health, and other related items.
- Private messaging: Study staff will send participants messages in Thrive4Life Connect to remind participants about when surveys open, send personalized resources, and answer any questions.

PROTOCOL TITLE: iThrive WI – A smartphone intervention for overdose and risk and COVID-19 among people who use drugs

- Data linkage to databases like the Wisconsin Immunization Registry, Medicaid, and Wisconsin hospitalization, emergency medical services, and infectious disease surveillance registries.

Optional activities include:

- Interactive modules about COVID-19 vaccines
- Sharing thoughts on discussion boards and private messaging others
- Engaging with online and local resources in the app
- Logs for motivation and thoughts of gratitude
- Using UW-Madison study team contact information.

See the study timeline/flowchart below for a detailed overview of when various activities will occur.

PROTOCOL TITLE: iThrive WI – A smartphone intervention for overdose and risk and COVID-19 among people who use drugs

13.3 After recruitment, study participants will be involved in the following procedures: eligibility screening, informed consent and study enrollment, baseline surveys, 12-week intervention session, 3-month follow-up surveys, and 6-month follow-up surveys.

PROTOCOL TITLE: iThrive WI – A smartphone intervention for overdose and risk and COVID-19 among people who use drugs

Recruitment, screening for eligibility, and informed consent and enrollment will follow the procedures previously described (See “Recruitment” and “Informed Consent” sections).

During the initial enrollment appointment and after providing informed consent, participants will complete the baseline survey and first of three daily check-ins (ecological momentary assessments).

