20.0 Study Analysis

PROTOCOL TITLE: iThrive WI – A smartphone intervention for overdose and risk and COVID-19 among people who use drugs

20.1 Primary Outcome Null hypothesis (feasibility): the study is feasible based on intervention content completion rates of at least 50%. Alternative hypothesis: fewer than 50% of intervention content is completed.

Secondary outcome null hypothesis #1 (preliminary effectiveness of overdose content): there is no difference in the number of days endorsing overdose risk behaviors per month at baseline vs. 3 months and baseline vs. 6 months. Alternative hypothesis: the frequency of overdose risk behaviors decreased from baseline to 3 months, and baseline to 6 months.

Secondary outcome null hypothesis #2 (preliminary effectiveness of COVID-19 content): there is no difference in proportion of participants who have been vaccinated against COVID-19 at baseline vs. 3 months and baseline vs. 6 months. Alternative hypothesis: the proportion vaccinated will increase from baseline to 3 months, and baseline to 6 months.

20.2 As a pilot feasibility study, the number of participants (n=60) reflects the maximum allowable participants in our budget and study timeframe. A formal sample size calculation was not done.

20.1 All participants who enroll in the study will be included in each analysis.

20.4 The average and variation in percentage of completed intervention modules and in the percentage completing each weekly intervention module over 12 weeks will be calculated and examined descriptively.

We will examine changes in the frequency of endorsing overdose risk behaviors and COVID-19 vaccination based on a descriptive analysis of the baseline, 3 month and 6 month surveys. We may also test for differences using appropriate statistical tests, including paired t-tests, McNemar's test, and models appropriate for count outcomes and repeated measures (Poisson or Negative Binomial Generalized Estimating Equations). As a pilot study, we expect that most analyses will be descriptive rather than inferential in nature.

20.5 We will examine weekly survey and intervention module completion rates. There are no stopping rules for efficacy or safety in this study.

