20.6 As a pilot feasibility study, we will examine missingness and survey completion as primary outcomes to assess engagement with intervention content and study feasibility. We may impute or use simple techniques such as last observed carried forward in analyses. We will track reported reasons for missing data such as loss of study phone, incarceration, withdrawal, etc.

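### Because only people who finish the baseline survey count as enrolled, consenters who do not finish it drop out of the feasibility denominators; this can bias completion and retention upwards, by an amount the documents do not give

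*Combined protocol and SAP*

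**What the plan says.** Section 4.3 gives the definition: "Enrolled participants are individuals who complete the baseline survey". The analysis-set item in section 20 (the second one numbered 20.1) then states: "All participants who enroll in the study will be included in each analysis". No other analysis set is named.

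Several feasibility measures rest on that set. The study summary in section 1.0 says: "We will examine feasibility outcomes based on study recruitment, retention, and intervention completion". The only threshold is in section 20.1, which holds that "the study is feasible based on intervention content completion rates of at least 50" per cent. Section 20.6 adds that "we will examine missingness and survey completion as primary outcomes to assess engagement with intervention content and study feasibility", without naming the surveys or the denominator. Section 13.2 lists the baseline survey among the required surveys.

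On the order of events, section 13.3 says: "During the initial enrollment appointment and after providing informed consent, participants will complete the baseline survey and first of three daily check-ins". The same section gives the sequence of procedures as "eligibility screening, informed consent and study enrollment, baseline surveys, 12-week intervention session, 3-month follow-up surveys, and 6-month follow-up surveys". Section 9.1 makes agreement at the consent checkbox the condition for reaching content in the app and does not mention the baseline survey as a condition. Section 5.1 keeps the screening data of everyone who consents. Section 5.3 keeps screening open until 60 participants are reached.

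**The concern.** The primary question is whether people will take up and stay with an app-based intervention. Under section 4.3 a person must finish the first study task before being counted at all. Someone who consents but stops during the baseline survey is an early feasibility failure, yet appears in neither the numerator nor the denominator of module completion or retention. Because that person does not count toward the 60, the place is filled by someone else and the plan provides no record of the loss.

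Two things are at stake. First, if such people exist and engage less than those who finish, the reported completion and retention are too high for the group to whom the study was actually opened. Second, the baseline survey can tell nothing about survey completion, because its rate is fixed at 100% among the enrolled.

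**Working it through.** **Step 1. Set the two uses of enrollment side by side.** Take a person who consents and does not finish the baseline survey.

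| | Section 4.3 | Sequence in section 13.3 |
|---|---|---|
| Enrolled? | No | Yes, at consent |
| In the section 20 analyses? | No | Yes |
| Counts toward the 60? | No | Yes |

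The denominator depends on which section is followed. Section 4.3 is the explicit definition, so it is the one used below.

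**Step 2. Inputs.** Planned enrolled number N = 60 (section 4.1), with up to 90 allowed (section 4.2). The feasibility bar is 50% (section 20.1). The plan has no calculation to reproduce: section 20.2 says that 60 reflects budget and timeframe. The documents give no rate of stopping between consent and baseline completion, so that share, f, is an assumption and is shown as a range.

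**Step 3. Formula.** Let p be content completion among the enrolled and q content completion among consenters who do not finish baseline. Completion among all consenters is (1 − f)p + fq, so the overstatement is f(p − q). It is zero if f = 0 or q = p. The worst case is q = 0, where completion among consenters is p(1 − f). With k extra consenters beyond the enrolled, f = k/(N + k), so k = Nf/(1 − f).

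**Step 4. Results at p = 50%, q = 0.**

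| f (assumed) | k with 60 enrolled | Completion among all consenters, 50% × (1 − f) | Completion needed among enrolled for 50% of consenters, 50%/(1 − f) |
|---|---|---|---|
| 0% | 0 | 50.0% | 50.0% |
| 2% | 1.2 | 49.0% | 51.0% |
| 5% | 3.2 | 47.5% | 52.6% |
| 10% | 6.7 | 45.0% | 55.6% |

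The percentages do not depend on N and are the same for 90 enrolled. In whole people with 60 enrolled:
- k = 1 gives 30/61 = 49.2%
- k = 3 gives 30/63 = 47.6%
- k = 6 gives 30/66 = 45.5%

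Retention follows the same arithmetic. Section 4.2 reports attrition of up to 50% in a prior study. If 50% of the enrolled are retained and non-finishers do not return, the third column applies unchanged.

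**Step 5. The baseline survey itself.** Among the enrolled its completion is 60/60 = 100%, whatever happens. Among consenters it would be 60/61 = 98.4%, 60/63 = 95.2% or 60/66 = 90.9% for k = 1, 3 or 6.

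**Step 6. Scale.** The 95% half-width for a proportion of 50% with n = 60 is 1.96 × √(0.25/60) = 0.127, or 12.7 points. A 5% loss shifts a 50% result by at most 2.5 points.

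**The case against.** The strongest reply is that the excluded group may be empty. The baseline survey comes straight after consent, at an in-person appointment run by a Prevention Specialist. It is multiple choice, participants may skip questions, and $20 is paid for completing it (sections 7.5, 8.1, 9.1, 13.3). Few people may stop there. This stands, and it is why the bias can only be called a risk.

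The zero-content assumption is also a worst case. Section 9.1 opens the app on consent, so a non-finisher could still use content. Equally, the text does not say that the weekly modules open before baseline is done, and section 13.1 places baseline before the 12-week intervention. Both points stand, and they leave q unknown.

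Recruitment is a separate feasibility outcome, and section 5.1 keeps the data needed to count consenters. So the loss could be reported, but the plan does not say that it will be.

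Three stronger readings are tempting and are not supported:
- A reader might infer that the definition does inflate completion or carries it over the 50% bar. The documents give no count of non-finishers and nothing on their use of content.
- A reader might infer that the fixed 100% raises an overall survey-completion rate. No section pools the baseline survey with the later ones, and section 20.6 can be read, with section 20.5, as meaning the weekly surveys.
- A reader might treat the first daily check-in in the same way, because it is scheduled for the same appointment. Section 4.3 conditions on the baseline survey only. A person can skip that check-in and still be enrolled, so it remains a measure that can be missed.

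**Conclusion.** The concern holds as a risk. Sections 4.3 and 20 together leave consenters who do not finish baseline out of the feasibility analyses, make baseline completion uninformative, and conflict with the sequence in section 13.3. The direction is upward if such people exist and engage less than the enrolled. The size cannot be determined from the documents: it is zero if nobody is lost, and at p = 50% it is at most 1.0, 2.5 or 5.0 points for a 2%, 5% or 10% loss. These shifts are well inside the sampling uncertainty at n = 60, and section 20.4 examines completion descriptively. They would matter mainly if the result fell close to the 50% bar. The point deserves correction because the people can be counted at almost no cost, not because a material bias has been shown.

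**What to change.** 1. Reconcile section 4.3 with section 13.3 so that enrollment has one meaning, and say what counts as a completed baseline survey given that questions may be skipped.
2. In section 20, compute module completion and retention with all consenters as the denominator (agreement in the app or documented verbal consent), and show the same figures for baseline completers alongside.
3. Report the numbers eligible, consented and baseline-completed, by site if convenient.
4. In section 20.6, name the surveys that make up survey completion: the 3- and 6-month surveys and the weekly surveys. Do not count the baseline survey as evidence. The first daily check-in need not be excluded.
5. Keep baseline completers as the set for change from baseline, where a baseline value is needed.

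The cost is a few sentences in sections 4.3, 13.3 and 20. No new data collection is needed, because section 5.1 already retains screening data for everyone who consents. If nobody is lost between consent and baseline, module completion and retention do not change. If some are, those figures may be slightly less favourable.
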